8.3.6.4 Landmark analysis

A landmark analysis of OS at specific timepoints (e.g. at 3 months) will be performed to assess any potential impact of MRD status on OS by treatment group and overall. For that, patients who completed induction therapy will be classified as per their MRD status at end of induction: MRD+, MRD-, MRD undetermined, MRD missing.

8.3.7 Time to neutrophil/platelet recovery

The time to neutrophil will be assessed for the following criteria:

- Number of days from start of treatment to the first day neutrophils $\geq 0.5 \times 10^9/L$.

- Number of days from start of treatment to the first day neutrophils $\geq 1.0 \times 10^9/L$.

Similarly, the time to platelet transfusion independent recovery will be assessed for the following criteria:

- Number of days from start of treatment to the first day platelets $\geq 50 \times 10^9/L$. This partial recovery will be considered only if no transfusion was provided within the last 48h preceding the partial platelet recovery (i.e. $\geq 50 \times 10^9/L$).
- Number of days from start of treatment to the first day platelets $\geq 100 \times 10^9/L$. Moreover, the time to adequate blood count recovery will be assessed as:
- Number of days from start of treatment to the first day platelets $\geq 50 \times 10^9/L$ and the first day neutrophils $\geq 1.0 \times 10^9/L$. Patients with platelet values $\geq 100 \times 10^9/L$ and neutrophils $\geq 1.0 \times 10^9/L$ prior to start of treatment will be excluded for this analysis.

Patient not meeting the recovery criteria mentioned above will be censored at last laboratory assessment. In case of no laboratory assessment, patient will be censored at start of Midostaurin. Patients who died, failed induction will be censored at maximum follow-up (i.e. LPLV). If patients reached recovery after HSCT, this will be taken into account and not censored at time of HSCT.

The analyses above will be repeated for induction and consolidation treatment phases.

Time to platelet and to neutrophil recovery will be plotted by treatment group along with their corresponding number of events, HR and 95% confidence intervals.

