4.2 Study phase (details of dosing in section 6)

The study contains three treatment phases:

- Induction treatment phase
- Consolidation treatment phase and,
- Post-consolidation treatment phase

A patient has to meet the following criteria to continue with the next treatment phase:

- A patient achieves CR at end of any treatment phase OR patient achieves CRi at end of any treatment phase **with adequate blood count recovery** defined as the following:
 - Complete Recovery in neutrophil count ($\geq 1 \times 10^9/L$)
 - Minimal recovery in platelet count ($\geq 50 \times 10^9/L$)

Of note, a patient not meeting the above criteria up to 93 days after start of induction phase is considered as “*induction failure*”. For details please see [Section 7.2.1.1](#).

The planned duration of an induction and consolidation cycle is 28 days. Upon adequate blood count recovery after day 28, midostaurin is stopped immediately (e.g., the evening dose of midostaurin or placebo on that day is not taken). Forty-eight hours thereafter is Day 1 (and start of chemotherapy) of the next cycle (Induction 2, Consolidation 1-4). At the end of the last consolidation cycle, i.e., prior to start of the post-consolidation cycle 1, midostaurin or placebo will not be interrupted. The duration of each post-consolidation cycle is 28 days.

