bid: twice daily; 1 cycle = 28 days, d: day(s); HSCT: Hematopoietic Stem Cell Transplantation; dauno: daunorubicin; ida: idarubicin; ^aHydroxyurea therapy allowed for ≤ 7 days; ^bMidostaurin/Placebo treatment from day 8 (Induction 1) and from day 4 (induction 2 and consolidation) until 48 hours prior to start of next treatment cycle; ^cAge ≥ 60: no daunorubicin / idarubicin in IND 2, cytarabine 1000mg/m²; ^d Patients in CR/CRi may proceed to HSCT at any time and will enter the post-consolidation after HSCT-recovery; ^e Patients in CRi must have adequate blood count recovery to move to next treatment phase

The study contains three treatment phases:

- Induction treatment phase
- Consolidation treatment phase
- Post-consolidation phase

A patient has to meet the following criteria to continue the next treatment phase:

- A patient achieves CR or CRi **with adequate blood count recovery** defined as the following:
 - Complete Recovery in neutrophil count (≥ 1 x 10⁹/L)
 - Minimal recovery in platelet count (≥ 50 x 10⁹/L)

Of note, a patient not meeting the above criteria up to 93 days after start of induction phase is considered as “*induction failure*”.

The **primary objective** is to determine if the addition of midostaurin to standard induction and consolidation therapy, followed by single agent post-consolidation therapy improves event-free survival (EFS) in patients with newly diagnosed FLT3-MN (SR < 0.05) AML.

The **primary endpoint** is EFS and is determined according to the IWG criteria for AML [Cheson et al 2003, ELN 2017 / Döhner et al 2017] as per investigator assessment. The final analysis was planned to be when a total of 285 EFS events are observed. The first and second interim analyses were planned after observing 40% and 75% of 285 EFS events, respectively.

The **key secondary objective** is to determine if the addition of midostaurin to standard induction and consolidation therapy, followed by single agent post-consolidation therapy improves overall survival (OS) in patients with newly diagnosed FLT3-MN (SR<0.05) AML.

The **key secondary endpoint** is OS. OS was to be initially hierarchically tested if EFS is significant in any of the interim and final analyses following a separate group-sequential plan using Haybittle-Peto stopping boundaries. Since the study was futile at the first interim analysis and therefore stopped due to futility, OS was not tested but will be analyzed and reported in the final clinical study report (CSR).

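### SAP 8.3.7 counts haematological recovery without a prior fall, so compliant patients already meet four of the five definitions when they enter consolidation

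*SAP*

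**What the plan says.** SAP 8.3.7 gives five definitions: neutrophils ≥0.5, neutrophils ≥1.0, platelets ≥50, platelets ≥100, and a combined criterion (platelets ≥50 with neutrophils ≥1.0), all × 10⁹/L. The first begins "Number of days from start of treatment to the first day neutrophils" and the others follow the same pattern, as does protocol 10.5.2.3. Neither section asks that the count should first have been below the threshold. The SAP adds "The analyses above will be repeated for induction and consolidation treatment phases", with hazard ratios and 95% confidence intervals.

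The one safeguard is a sentence after the combined criterion. Patients with platelets ≥100 and neutrophils ≥1.0 "prior to start of treatment will be excluded for this analysis". For platelets ≥50, the SAP also says "This partial recovery will be considered only if no transfusion was provided within the last 48h preceding the partial platelet recovery".

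Entry to consolidation is gated. Protocol 4.2 states "A patient has to meet the following criteria to continue with the next treatment phase", namely CR, or CRi with neutrophils ≥1 and platelets ≥50 × 10⁹/L. SAP section 2 repeats this: "A patient has to meet the following criteria to continue the next treatment phase". Protocol 7.2.1.1 applies the same test before each later consolidation cycle. Where a cycle is prolonged past Day 28 for count recovery, protocol 4.2 says "Forty-eight hours thereafter is Day 1 (and start of chemotherapy) of the next cycle".

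**The concern.** Time to neutrophil recovery and time to platelet recovery are two named secondary objectives (protocol Table 3-1), and SAP 8.3.7 keeps them for the final report. An event rule that patients satisfy on arrival cannot show how long counts take to recover after chemotherapy.

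A hazard ratio near 1.00 from such a rule could be read as no prolongation of recovery. That is what protocol 1.2.1.2 reports for the earlier trial in FLT3-mutated AML, and protocol 2.3 says the present trial doses midostaurin for longer within each cycle. The transfusion summaries (SAP 8.3.8) and the laboratory shift tables (SAP 9.3) do not give time to recovery, so they would not fill the gap.

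**Working it through.** The documents give no figure for time to recovery, so there is none to reproduce.

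**1. Entry counts against the five definitions.** Inputs: the gate in protocol 4.2 and SAP section 2, and Table 7-2 (CR has platelets ≥100; CRi with adequate recovery has platelets 50 to <100).

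| Definition (× 10⁹/L) | CRi at lowest permitted counts (1.0 / 50) | CR at lowest counts (1.0 / 100) |
|---|---|---|
| Neutrophils ≥0.5 | met | met |
| Neutrophils ≥1.0 | met | met |
| Platelets ≥50 | met | met |
| Platelets ≥100 | not met | met |
| Platelets ≥50 and neutrophils ≥1.0 | met | met |
| Total | 4 of 5 | 5 of 5 |

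The 48-hour transfusion condition on platelets ≥50 does not alter this, because protocol 7.2.1.6 already applies a two-day transfusion-free convention to these responses.

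**2. The exclusion.** Start of study treatment is the first dose of any component (SAP 3.5), which is induction Day 1. Taken literally, the exclusion does nothing at consolidation entry. If it is re-based there, it removes CR patients. Those left (neutrophils ≥1.0, platelets 50 to <100) still meet the other four definitions. Its platelet limit is also 100, whereas the combined criterion it follows uses 50.

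**3. Consolidation Day 1 clock, entrants only, count at Day 1.** All events tie. With n₁ and n₀ patients, the Breslow score equation is n₁ − (n₁ + n₀)·n₁eᵇ/(n₁eᵇ + n₀) = 0, so eᵇ = 1. Efron gives the same. With n per arm the information is 2n × ¼, so SE = 2/√(2n):

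- n = 50: SE 0.200, HR 1.00 (0.68 to 1.48)
- n = 75: SE 0.163, HR 1.00 (0.73 to 1.38)
- n = 100: SE 0.141, HR 1.00 (0.76 to 1.32)

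Numbers entering consolidation are not given, so n is an assumed range. If qualifying counts are spread at random over four days, unrelated to arm, the average HR is still 1.00.

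**4. If some entrants lack a qualifying count.** This was simulated with assumed inputs: 150 per arm, recovery at Day 14 plus an exponential time (control mean 10 days), censored at Day 50. With 5%, 10% or 20% lacking an entry count, a true HR of 0.7 appears as 0.99, 0.97 or 0.93, and a true HR of 0.5 as 0.98, 0.95 or 0.89. Requiring a prior fall returns 0.72 and 0.51.

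**5. Two other readings.**

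- Clock from induction Day 1, events counted in consolidation: the event day is the day of entry. An assumed HR of 0.7 for time to entry returns 0.70.
- Induction failures kept and censored at the last patient's last visit, as SAP 8.3.7 says for patients who died or failed induction: the Breslow HR is the ratio of numbers entering. With 251 per arm (502/2) and assumed entry of 75% against 65%, 188/163 = 1.15 (Efron 1.28). With 80% against 60%, 201/151 = 1.33 (Efron 1.64).

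Neither measures count recovery.

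**6. Induction.** The clock starts with chemotherapy, but randomisation and the first midostaurin or placebo dose are on Day 8 (protocol 4.1). A patient who presents above a threshold is counted as recovered before randomisation. The share of such patients is not given.

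**7. Origins.** For neutrophils ≥0.5 and platelets ≥50, Table 3-1 and SAP section 2 start at the first day of a chemotherapy cycle, but SAP 8.3.7 starts at the start of treatment. For neutrophils ≥1.0 and platelets ≥100 the origins agree in induction.

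**The case against.** A reader might infer that the consolidation hazard ratio is 1.00 by construction, without conditions. The documents do not support that. It needs a consolidation Day 1 clock, entrants only, and a count at or near Day 1, and the SAP specifies none of these. Response is assessed between Days 21 and 28, so a qualifying count can precede the next Day 1 by a week or so. Tie handling is not stated either; an exact or discrete likelihood with everyone tied is flat and gives no estimate. All of this stands, but the other readings do no better.

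The reach is narrower than five endpoints. In Table 3-1 only neutrophils ≥0.5 and platelets ≥50 have a per-cycle origin. Neutrophils ≥1.0 and platelets ≥100 run from induction Day 1, and the combined criterion is not listed. The consolidation repeats of those three are additions by the SAP. This stands.

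An artefact might also be noticed. The SAP calls for plots and event numbers and the protocol for medians, so a curve that drops at once would look odd. That limits the risk of false reassurance but does not supply the missing estimate.

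It can be said that any programmer would take recovery to imply a nadir. The text points the other way: the authors saw that some patients start above threshold and dealt with it by a baseline exclusion. The SAP appendices refer to an original SAP that is not available here, so some derivation detail may sit there.

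**Conclusion.** The point holds. As written, the rule counts recovery without a prior fall, and the plan's own entry gate means compliant patients meet four of five definitions on entering consolidation, or all five if in CR. That count rests on the documents alone. HR 1.00 holds for the four definitions under the three conditions named above and Breslow or Efron ties. None of the readings tested measures haematological recovery in consolidation. In induction the same gap lets events precede randomisation, to an extent that cannot be sized from the documents.

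Two further inferences are not supported. Nothing here shows that midostaurin delays recovery: protocol 2.3 reports no association of plasma exposure with duration of neutropenia. Nor does the point touch the main results. SAP 8.3 makes the secondary efficacy endpoints descriptive, without p-values, and EFS, OS and the futility decision do not use these definitions. Severity is low to moderate.

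**What to change.** Amend SAP 8.3.7 as follows.

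- **Event.** Recovery is the first value at or above the threshold after a documented post-chemotherapy value below that same threshold in the cycle analysed. This replaces the pre-treatment exclusion.
- **Origin.** Use Day 1 of that cycle for every consolidation analysis, and for neutrophils ≥0.5 and platelets ≥50 in any phase. Keep induction Day 1 for neutrophils ≥1.0 and platelets ≥100 in induction.
- **Analysis set and censoring.** Limit the consolidation repeat to patients who start the cycle; induction failures do not belong in it. State which cycle or cycles are analysed and how deaths are handled in each phase.
- **Never-below patients.** Tabulate them by arm, with a sensitivity analysis that counts them as recovered at Day 1.
- **Transfusion.** Apply the 48-hour window to both platelet criteria and to the platelet part of the combined criterion. The SAP already introduces the platelet criteria with "the time to platelet transfusion independent recovery will be assessed for the following criteria", but states the window for platelets ≥50 only.
- **Record.** Enter this in SAP section 11, which at present reports no change from the protocol analyses, as a change to the event definition made after unblinding.

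The work is a few sentences and one derivation, using counts the trial already collects. There are two real costs. The rule is set after unblinding, as SAP section 1 says of its other final-analysis decisions. The main estimate also conditions on a fall that occurs after randomisation and may depend on treatment, which is why the never-below table and sensitivity analysis are needed.

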Other **secondary** [REDACTED] **objectives** are:

Objective	Endpoint
To compare CR + CRi with adequate blood count recovery rate in the two treatment groups.	CR and CRi with adequate blood count recovery rate according to the International Working Group (IWG) for AML [Cheson et al 2003, ELN 2017 / Döhner et al 2017] as per investigator assessment.
To compare the percentage of patients who reached CR or CRi with adequate blood count recovery with MRD negative bone marrow in the two treatment groups.	Percentage of patients with CR or CRi with adequate blood count recovery with MRD negative bone marrow.
To compare the time to MRD- between the two treatment arms in the two treatment groups.	Number of days from date of randomization to first documented MRD-
To compare the percentage of patients with MRD negative status in the post-consolidation phase in the two treatment groups.	Percentage of patients with MRD negative status during post-consolidation Phase
To compare DFS, as well as the Cumulative Incidence of Relapse (CIR) and Cumulative Incidence of Death (CID) in the two treatment groups.	
DFS, as measured from the date of first CR or CRi with adequate blood count recovery to relapse or death from any cause, whichever occurs first.
 
CIR is defined for patients with CR or CRi with adequate blood count recovery: time from achieving CR or CRi with adequate blood count recovery until onset of relapse. Patients without relapse are censored at the last adequate response assessment. Patients who died without relapse are counted as a competing cause of failure.
 
CID is defined for patients with CR or CRi with adequate blood count recovery: time from achieving CR or CRi with adequate blood count recovery until death. Patients who did not die are censored at the last contact date. Patients who relapsed are counted as a competing cause of failure.

To compare the time to CR or CRi with adequate blood count recovery in the two treatment groups.	Number of days from date of randomization to first documented CR or CRi with adequate blood count recovery.
To compare the time to neutrophil recovery in the two treatment groups.	
Number of days from the first day of a chemotherapy cycle to first day neutrophils $\geq 0.5 \times 10^9/L$.
 
Number of days from day 1 of commencing induction therapy to first day neutrophils $\geq 1.0 \times 10^9/L$.

Objective	Endpoint

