To compare the time to platelet recovery in the two treatment groups.	Number of days from the first day of a chemotherapy cycle to first day platelets $\geq 50 \times 10^9/L$. Number of days from day 1 of commencing induction therapy to first day platelets $\geq 100 \times 10^9/L$.
To assess the safety and tolerability of midostaurin in combination with chemotherapy and as monotherapy during post-consolidation.	Frequency/severity of AEs, and laboratory abnormalities.
To further characterize the pharmacokinetics of midostaurin, CGP52421 and CGP62221.	Plasma concentrations and pharmacokinetic parameters for midostaurin, CGP52421 and CGP62221.
To assess the impact of midostaurin on health related quality of life and AML symptom reduction.	Change from baseline score for each time point for the FACT-Leu and the EQ5D-5L (visual analogue scale (VAS)) by treatment arm.

[REDACTED]

[REDACTED]

[REDACTED]

[REDACTED]

[REDACTED]

[REDACTED]

[REDACTED]

[REDACTED]

[REDACTED]

[REDACTED]

[REDACTED]

[REDACTED]

[REDACTED]

Data analysis general information

The statistical analysis of this study will be performed by Novartis. SAS® version 9.4 or later (SAS Institute Inc., Cary, NC, USA) will be used for all analyses. All data are part of the Clinical Database and will be exported to SAS® files for analysis. EAST version 6.4 or later (Cytel Inc.®) will be used to determine stopping boundaries in the group sequential plan.

The final EFS analysis was supposed to be performed by Novartis. However, since the study was stopped at first interim analysis only an updated EFS analysis will be provided in the final CSR. The first interim analysis of EFS was performed by an independent external statistician and an independent external programmer (CRO not involved with the conduct of the study). The study was stopped at this first interim and no further analyses are to be performed (i.e. study stopped).

The study will end when the last ongoing patient will have completed or discontinued treatment.

All events with start date before or on the cut-off date and end date after the cut-off date will be reported as 'ongoing'. The same rule will be applied to events starting before or on the cut-off date and not having documented end date. This approach applies, in particular, to adverse event and concomitant medication reports. For these events, the end date will not be imputed and therefore will not appear in the listings.

General analysis conventions

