3.5 Date of first administration of study treatment

The date of first administration of study treatment is derived as the first date when a non-zero dose of any component of study treatment was administered and recorded on the exposure eCRF. For example, if the 1st dose of study drug A is administered on 04Jan2019, and the 1st dose of its combination partner, drug B, is administered on 03Jan2019, the date of the first administration of study treatment is on 03Jan2019). The date of the first administration of study treatment will also be referred as the *start of study treatment*.

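### SAP 8.3.7 and protocol 10.5.2.3 time recovery to neutrophils ≥0.5 and platelets ≥50 from the start of treatment, but the endpoint tables time it from the first day of a chemotherapy cycle, and the consolidation repeat has no stated origin

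*SAP*

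**What the plan says.** **Endpoint tables.** Protocol Table 3-1 and the objectives table in SAP section 2 use two origins. For neutrophils ≥0.5 × 10⁹/L the endpoint is "Number of days from the first day of a chemotherapy cycle to first day neutrophils" reach that level, and for platelets ≥50 × 10⁹/L it is "Number of days from the first day of a chemotherapy cycle to first day platelets" do so. For neutrophils ≥1.0 it is "Number of days from day 1 of commencing induction therapy to first day neutrophils" reach it, and for platelets ≥100 it is "Number of days from day 1 of commencing induction therapy to first day platelets" reach it.

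**Analysis sections.** SAP 8.3.7 uses one origin throughout. Both neutrophil criteria read "Number of days from start of treatment to the first day neutrophils" and both platelet criteria "Number of days from start of treatment to the first day platelets". The combined criterion (platelets ≥50 and neutrophils ≥1.0) has the same origin. Protocol 10.5.2.3 also starts all of these at the start of treatment. SAP 8.3.7 then adds: "The analyses above will be repeated for induction and consolidation treatment phases". It names no origin for the repeat.

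**Meaning of the term.** SAP 3.5 derives the start of study treatment as "the first date when a non-zero dose of any component of study treatment was administered", which is Day 1 of induction chemotherapy. SAP Table 8-2 refers to one 93-day window as running both from the start of chemotherapy and from the start of treatment. SAP section 11 declares no change from the protocol's analyses.

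**The concern.** The two definitions of ≥0.5 and ≥50 cannot both be programmed. The endpoint table implies a recovery time for each chemotherapy cycle. The analysis section gives one time per patient, measured from induction Day 1.

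Where the definitions differ, the analysis variable contains the length of earlier cycles as well as recovery after the current one. That extra time varies between patients with the number of inductions and how far each was prolonged for count recovery. It is not a constant shift, so it does not drop out of the hazard ratio that SAP 8.3.7 plots by treatment group. The number of inductions depends on response, so the extra time may also differ between arms.

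The comparison matters for interpretation. Protocol 1.2.1.2 reports that midostaurin did not prolong count recovery in the induction and consolidation phases of the earlier phase III trial. Protocol 2.3 says this trial doses midostaurin for longer within each cycle than that trial did.

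**Working it through.** **Inputs**
- Planned induction or consolidation cycle: 28 days (protocol 4.2).
- Maximum Induction 1: 28 + 14 + 1 = 43 days (protocol 6.1.5).
- Maximum Induction 2 and maximum consolidation cycle: 28 + 21 + 1 = 50 days each (protocol 6.1.5).
- Four consolidation cycles after one induction, three after two (protocol 4.2.1).
- Counts needed to enter the next phase: neutrophils ≥1.0 and platelets ≥50 (protocol 4.2, SAP section 2).

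**The plan's own figure.** Protocol 7.2.1 limits the induction phase to 93 days: 43 + 50 = 93. It reproduces.

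**Thresholds ≥1.0 and ≥100.** Induction Day 1 is the start of treatment, so the two definitions agree.

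**Induction, thresholds ≥0.5 and ≥50.** For a patient who first reaches the threshold in Induction 2:

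excess = (Day 1 of Induction 2) − (Day 1 of Induction 1) = length of Induction 1 = 28 to 43 days.

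For illustration, assume recovery on cycle day 25. If Induction 2 starts on study day 29, the start-of-treatment clock gives 29 + 25 − 1 = 53. If it starts on study day 44, it gives 44 + 25 − 1 = 68. The endpoint table gives 25 both times. The lower limit of 28 is not firm, because protocol 6.1.1.1 lets Induction 2 begin 48 hours after persistent blasts are known from a Day 21–28 marrow.

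**Consolidation, thresholds ≥0.5 and ≥50.** Three readings are possible.

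1. *Literal.* The clock starts at induction Day 1 and stops at the first qualifying count. Patients enter consolidation with neutrophils ≥1.0 and platelets ≥50, so that count normally falls in induction. No consolidation recovery time results.
2. *Induction Day 1 origin, search limited to the consolidation cycle.* Excess in cycle c = induction duration + (c − 1) × consolidation cycle length, with 28 days (shortest) or 50 days (longest) per consolidation cycle.
3. *Origin at the start of the consolidation phase.* Excess in cycle c = (c − 1) × 28 to (c − 1) × 50.

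| Consolidation cycle | Reading 2, one induction | Reading 2, two inductions | Reading 3 |
|---|---|---|---|
| 1 | 28–43 | 56–93 | 0 |
| 2 | 56–93 | 84–143 | 28–50 |
| 3 | 84–143 | 112–193 | 56–100 |
| 4 | 112–193 | not given | 84–150 |

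All values are days. Under reading 2 the excess is 28–93 days in cycle 1 and reaches 193 days in the last cycle. With the maximum lengths in SAP 6.7.1 (42, 49 and 49 days) these maxima become 42 + 49 = 91 and 42 + 3 × 49 = 189 days.

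**Cycle Day 1 origin alone.** Patients entering consolidation are already above 0.5 and 50. Counting from cycle Day 1 to the first qualifying count could therefore return recovery on Day 1, before any nadir. The cycle-based definition also needs a condition that the count has first fallen below the threshold.

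**The case against.** The best defence is that repeating the analyses by phase implies a clock restarted at each phase. An unchanged clock would make the consolidation repeat nearly empty, so this reading is natural, and it leaves no excess in consolidation cycle 1. A reader might infer that consolidation recovery times as a whole are overstated by 28 to 93 days. The documents do not support that. The range fits cycle 1 only, and only if the origin stays at induction Day 1 while the search is limited to consolidation, a combination the SAP nowhere states.

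The phase-start reading does not remove the conflict. SAP 8.3.7 does not state it, and it leaves 28–150 days in consolidation cycles 2 to 4 and the full excess in Induction 2. It also fits one sentence of 8.3.7 poorly: patients with platelets ≥100 and neutrophils ≥1.0 before the start of treatment are excluded from the combined analysis. With a reset clock, that would remove patients who enter consolidation with full count recovery.

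A reader might also infer that the arm with more second inductions must appear slower to recover, and size this from the phase IB remission figures in protocol 1.2.1.2. Those figures are remission proportions, not second-induction rates, and neither document gives an expected second-induction rate by arm. Moreover, SAP 8.3.7 censors patients who failed induction at maximum follow-up, so those who never recover contribute no inflated recovery time. A difference between arms is possible, but its direction and size cannot be derived.

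Two further points stand. The conflict already exists within the protocol, and the SAP carries it forward. The endpoint is also one of several secondary endpoints, in a trial already stopped for futility.

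**Conclusion.** The inconsistency is real and confined to neutrophils ≥0.5 and platelets ≥50. Following SAP 8.3.7 as written does not deliver the endpoint in Table 3-1 and SAP section 2.

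The firmest consequence is in induction: a patient who first recovers in Induction 2 is overstated by the length of Induction 1, about 28 to 43 days, or somewhat less if Induction 2 starts early. In consolidation the consequence depends on which of the three readings is programmed. The defect there is an undefined origin with widely different results, not a known overstatement. The figures assume that the protocol's planned and maximum cycle lengths are kept.

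SAP section 8.3 limits these endpoints to descriptive summaries without p-values. Alpha, power, EFS and OS are unaffected. The correction should be made because a hazard ratio for recovery is still to be reported.

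**What to change.** In SAP 8.3.7 and protocol 10.5.2.3:

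- Time neutrophils ≥0.5 and platelets ≥50 from Day 1 of each chemotherapy cycle, and report them per cycle.
- Count recovery only after the count has fallen below the threshold in that cycle, and say how patients who never fall below it are handled.
- Keep induction Day 1 as the origin for neutrophils ≥1.0 and platelets ≥100.
- State the origin for the combined criterion, which the endpoint tables do not define, and for every criterion kept in the consolidation repeat.
- Record the alignment in SAP section 11, which now declares no change.

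The cost is a few lines of text, a different start-date variable and one added condition in the program. No new data are needed for the origin, since SAP 6.2 already takes cycle Day 1 dates from the visit panel.
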